7.5.2 Cardiotoxicity

A theoretical risk of nucleosides is mitochondrial toxicity that can manifest as cardiac toxicity/congestive heart failure. Surveillance for this theoretical risk will be done in this study via assessments of AEs, ECGs and echocardiograms, which will be obtained at specified timepoints during the treatment period in this study.

In order to effectively monitor for potential treatment-related cardiotoxicity during the study, subjects presenting at screening must have:

- ECG PR interval must be < 200 msec and there must be no evidence of any conduction blocks.
- echocardiogram ejection fraction (EF) must be $\geq 55\%$.

During the treatment period, emergence of or changes in symptoms or clinically significant findings in ECG may trigger the following stopping criteria:

If a first degree AV block is diagnosed and:

- The PR interval is > 200 msec but ≤ 240 msec, study drugs can be continued. Close monitoring with weekly ECG is recommended.
- The PR interval is > 240 msec but ≤ 300 msec (confirmed by a repeat triplicate analysis at least 30 minutes after the initial assessment), an assessment of the subject's clinical status, including symptoms, physical examination and other clinical parameters should be made. Based on this assessment, the study drugs may or may not be continued. Close monitoring with weekly ECG is recommended.

- The PR interval is >300 msec (confirmed by a repeat triplicate analysis at least 30 minutes after the initial assessment, irrespective of presence or absence of clinical symptoms), ODV must be discontinued. The Investigator and Sponsor Medical Monitor must determine whether or not continued dosing with AL-335 and SMV is acceptable for subjects that discontinue ODV.
- If a second degree or higher AV block is diagnosed (confirmed by a repeat triplicate analysis at least 30 minutes after the initial assessment and irrespective of presence or absence of clinical symptoms), ODV must be discontinued. The Investigator and Sponsor Medical Monitor must determine whether or not continued dosing with AL-335 and SMV is acceptable for subjects that discontinue ODV.

All study medications must be discontinued:

- In asymptomatic patients with no clinical evidence of congestive heart failure:
 - If the absolute decline from baseline in EF is >10% AND the post-baseline EF is <50%; e.g., 60% →49%)

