NOTE: For asymptomatic subjects without clinical evidence of heart failure, but with an apparent decline in EF of >10%, an urgent repeat echocardiogram may be performed to confirm the finding. If confirmed and <50%, all study drugs should be discontinued as described above. If the confirmatory EF is ≤10%, the Investigator and Medical Monitor should perform a cardiology assessment (see below) and, based on the subject's overall clinical picture, decide whether or not to discontinue study drug.

- If the absolute decline from baseline in EF is >5% and ≤10%, an urgent unscheduled visit must occur for the assessment of the subject's clinical status, including symptoms, physical exam, and other clinical parameters. This assessment should occur before deciding whether to stop or continue study drugs.
- In symptomatic subjects (e.g., dyspnea, orthopnea) or subjects with signs of congestive heart failure (e.g., S3 gallop, pedal edema, pulmonary edema):
 - If the absolute decline from baseline in EF is ≥5% (e.g., 61%→54%)
 - The Investigator and Sponsor Medical Monitor may also deem it necessary to discontinue study drug in symptomatic subjects with an absolute decline from baseline in EF of <5%
- In asymptomatic or symptomatic subjects with clinical evidence of heart failure:
 - If absolute decrease in EF from screening is >10%, these subjects must undergo mandatory assessment (see below) and have an urgent cardiology referral; the EF decrease must be reported to the Medical Monitor within 24 hours so that the clinical case and workup and treatment strategy can be discussed.

Subjects with an absolute decrease from screening of $>5\%$ to $\leq 10\%$ in LVEF must have an urgent unscheduled visit for further assessment as soon as possible.

The cardiology assessment should include, but is not limited to, the following:

- Cardiopulmonary review of systems and physical examination,
- Troponin I assessment - (serial assessments may be indicated)
- BNP or Pro-BNP (serial assessments may be indicated)
- 12-lead ECG and
- Additional echocardiography (at study approved facility) – if clinically indicated, at a frequency determined by the Investigator’s judgment.

Echocardiography must be performed at study approved facility on any subject who develops symptoms or signs of possible congestive heart failure (e.g., dyspnea, orthopnea, S3 gallop, pedal edema) during the study, regardless of the timing of such symptoms, including during the Follow-up Period.

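### Protocol 7.5.2, NOTE: the repeat-echo threshold is set on the EF itself, so the cardiology-assessment branch can never operate, and the NOTE gives no action for a confirmed EF fall of more than 10 points with EF still at or above 50%

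*Protocol*

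**What the plan says.** All of this is in Protocol 7.5.2 and concerns falls in absolute EF points.

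- **Stopping rule, no symptoms and no evidence of heart failure:** "If the absolute decline from baseline in EF is >10% AND the post-baseline EF is <50"%. The worked example is 60% to 49%.
- **NOTE, same subjects, apparent fall of more than 10 points:** "an urgent repeat echocardiogram may be performed to confirm the finding". Two outcomes follow. The first is "If confirmed and <50%, all study drugs should be discontinued as described above". The second is "If the confirmatory EF is ≤10%, the Investigator and Medical Monitor should perform a cardiology assessment (see below"), after which study drug is continued or stopped on the overall clinical picture.
- **Smaller fall, same subjects:** "If the absolute decline from baseline in EF is >5% and ≤10%, an urgent unscheduled visit must occur".
- **Later bullet:** it opens "In asymptomatic or symptomatic subjects with clinical evidence of heart failure" and its action is "If absolute decrease in EF from screening is >10%, these subjects must undergo mandatory assessment (see below) and have an urgent cardiology referral", with a report to the Medical Monitor within 24 hours. The sentence after it begins "Subjects with an absolute decrease from screening of" more than 5 and up to 10 points, and calls for an urgent unscheduled visit.

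Protocol 4.3 excludes anyone with a screening EF below 55%, and 7.5.2 repeats that floor.

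**The concern.** A threshold of 10% makes sense for a fall in EF. It makes no sense for an EF in an enrolled subject. Everywhere else in 7.5.2 the figure of 10% is a cut-off on the decline.

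Once that sentence fails, the NOTE has only one working outcome: confirmed and below 50%. A subject whose fall of more than 10 points is confirmed but whose EF stays at or above 50% has no instruction there. Whether the section supplies one elsewhere depends on how the later bullet is read.

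The rule matters because Protocol 1.3 names the heart as a target organ of odalasvir toxicity. In the 26-week dog study (1.3.1) the EF reduction was minor and stayed within the normal range, alongside progressive left ventricular dilatation. A sizeable fall that does not cross 50% is therefore a signal the site instruction should handle explicitly.

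**Working it through.** No distribution is assumed. Decline = baseline EF − repeat EF, in points. SAP 8.3.3 takes screening as the echocardiogram baseline, so falls from baseline and from screening are the same quantity.

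**1. The protocol's own examples.** 60 − 49 = 11, which exceeds 10, and 49 is below 50: the stopping rule is met, as stated. For symptomatic subjects, 61 − 54 = 7, which is at least 5: also as stated.

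**2. The NOTE's second outcome, read literally.** Baseline is at least 55 and repeat EF at most 10, so the decline is at least 55 − 10 = 45, and EF is below 50. Both stopping conditions hold for every such value. The assessment branch is empty. If it could be reached, it would make optional a stop that the sentence before it requires.

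**3. Where the unassigned case lies.** It needs decline > 10 and EF ≥ 50. Adding the two gives baseline > 60. In whole points the EF runs from 50 to baseline − 11, which is (baseline − 11) − 50 + 1 = baseline − 60 values:

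| Baseline EF | Values | EF range |
|---|---|---|
| 55% or 60% | 0 | none |
| 61% | 1 | 50 |
| 65% | 5 | 50–54 |
| 70% | 10 | 50–59 |

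**4. What each candidate intent would do to the NOTE.**

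| Repeat result | If the decline was meant (≤10 points) | If confirmed with EF ≥50% was meant |
|---|---|---|
| Decline >10, EF <50% | stop | stop |
| Decline >10, EF ≥50% | unassigned | assess, then decide |
| Decline ≤10 | assess, then decide | unassigned in the NOTE |

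Either single-phrase correction leaves one outcome unwritten. In the right-hand column, the separate urgent-visit rule still covers declines above 5 and up to 10.

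**5. The later bullet, read both ways, at baseline 65% with no symptoms or signs.**

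| Fall | EF | Heart-failure phrase limits only the symptomatic group | Heart-failure phrase limits both groups |
|---|---|---|---|
| 6–10 | 59–55 | urgent visit | urgent visit |
| 11–15 | 54–50 | assessment, urgent referral, 24-hour report | nothing specific required after confirmation |
| 16 or more | 49 or less | stop | stop |

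On the narrow reading the required response weakens between 55% and 54% and returns at 49%.

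**6. Other cover.** The EF trigger in 4.7.1 needs EF below 50%. Section 4.6.1 refers back to 7.5.2 or leaves the matter to the investigator's safety judgement. Section 6.2.6 says whose reading guides decisions, not what to do.

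**The case against.** The strongest reply is that the later bullet already handles the case. On the narrow reading its mention of asymptomatic subjects does little work, since naming subjects with evidence of heart failure would have been enough. Subjects with signs of heart failure must already stop at a fall of 5 points or more. The next sentence sets the lower tier for subjects without restriction and uses the same screening reference, which suggests one population with two tiers. This argument largely stands: the inclusive reading is the more likely one, and under it no value in step 3 is without a required action.

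It does not make the wording safe. Elsewhere 7.5.2 treats symptoms and clinical evidence of heart failure as separate attributes, so signs without symptoms is a coherent group, and a site could reasonably take the bullet to mean that group.

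A second reply is that placing the threshold on the decline is a guess. That also stands. It would send a repeat echo showing no fall at all to cardiology assessment, and the order of the sentences fits the other intent as well.

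A reader might also count every repeat value that reaches no NOTE branch as the size of the problem: 16 at baseline 65% (EF 50–65). The documents do not support that. Eleven of those values are falls of 0–10 points, where the alarm was not confirmed, and falls of 6–10 already require an urgent visit. Only 5 are the case at issue.

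**Conclusion.** The threshold in the NOTE is wrong as written, with certainty, given the entry floor of 55%. The NOTE also assigns no action to a confirmed fall of more than 10 points with EF at or above 50%, a case that exists only for baseline EF above 60%.

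It is tempting to go further and say that the protocol as a whole leaves such subjects without a required response. The documents do not support that: it is true only on the less likely reading of the later bullet. Nor do they settle which wording was intended.

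The point is minor. Most sites would probably act as intended, EF is read centrally, and neither reading requires stopping in this cell. Protocol 1.3.1 reports no echocardiographic safety signal in humans to date. The SAP tabulates and lists EF declines above 10% whatever EF is reached, so no analysis changes. The number of subjects affected cannot be estimated from the documents.

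**What to change.** 1. Replace the NOTE's outcome sentences with three explicit branches:
   - decline above 10 points confirmed and EF below 50%: stop all study drugs;
   - decline above 10 points confirmed and EF at or above 50%: mandatory cardiology assessment, urgent referral and 24-hour report, then decide on study drug;
   - repeat decline of 10 points or less: cardiology assessment if the sponsor confirms that this was the intent; otherwise follow the existing urgent-visit rule for falls above 5 and up to 10 points.
2. Reword the later bullet so that it applies to every subject with a decrease above 10 points, with or without symptoms or clinical evidence of heart failure, in addition to the stopping rules.

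The first two branches are right under either intent; only the third needs the sponsor's answer. The cost is a wording change in one section, with no new type of procedure. The downside is some extra cardiology referrals caused by echo measurement noise.

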7.5.3 Prolonged QTc (i.e., >500 msec or change from baseline of >60 msec)

If a post-baseline QTc is found to be prolonged to >500 msec or if there is a change from baseline of >60 msec in repeat ECG assessments (e.g., triplicate ECGs) and this change is deemed clinically significant, all study drugs should be discontinued. Additional cardiac workup may be performed at the discretion of the Investigator. Any subject with prolonged QTc should be advised to discontinue and avoid any medications known to prolong QTc. In addition, serial ECGs (approximately weekly) should be assessed until the subject’s QTc has returned to baseline.

7.5.4 Renal Safety Monitoring

Renal safety will be monitored by evaluating urine dipstick leukocyte esterase, serum creatinine levels, eGFR and serum chemistry results. The investigator should closely monitor for clinically relevant changes in serum creatinine and eGFR. In case renal complications develop, subjects must be treated as clinically appropriate. Dosing may continue if the renal complication is considered not to be related to study drug in the opinion of the investigator.

For eGFR monitoring, the following guidance should be followed:

- If the eGFR value is <30 mL/min/1.73m², the value must be confirmed by repeat testing during an unscheduled visit, preferably within 1 week after the results become available to the study site.
- If the eGFR value is confirmed to be <30 mL/min/1.73m², all study drugs must be interrupted and renal function should be followed as clinically appropriate.

Recommencement of treatment should be discussed with the Sponsor on a case-by-case basis.

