4.6.1 Subject Treatment Discontinuation Criteria

If a subject's study drug treatment must be discontinued before the end of the treatment regimen, this will not result in automatic withdrawal of the subject from the study.

A subject's study drug treatment (AL-335, SMV and ODV) must be permanently discontinued if:

- The investigator believes that for safety reasons (e.g., AE), it is in the best interest of the subject to discontinue study drug treatment.
- The subject becomes pregnant.
- The subject has evidence of muscle injury (Section 7.5.1) or cardiac toxicity (Section 7.5.2 and 7.5.3).
- The subject has a Grade 4 rash; see Section 7.6.
- The subject has a Grade 3 or 4 allergic reaction; see Section 7.7.
- The subject has a confirmed Grade 4 ALT and/or AST value that is $>2\times$ the baseline value; see Section 7.9.
- The subject has a confirmed Grade 4 bilirubin value which is considered a sign of worsening liver disease, or for which there is no identifiable explanation; see Sections 7.8 and 7.9.
- The subject has severe worsening of hepatic disease.
- The subject has a confirmed diagnosis of pancreatitis.
- The subject has a Grade 4 AE or laboratory abnormality at least possibly related to 1 of the study drugs and which is considered clinically significant (laboratory abnormalities only).
- The subject requires treatment with any of the medications reported on the list of disallowed medications; see Section 5.12.
- The subject experiences inadequate virologic response or viral breakthrough (refer to Definitions)
- An event occurs which triggers the study treatment stopping criteria (Section 4.7.1)

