Bilirubin Direct Bilirubin¹⁴, High > 28 days of age	NA	NA	> ULN	> ULN with life-threatening consequences (e.g., signs and symptoms of liver failure)
\leq 28 days of age	ULN to \leq 1 mg/dL	> 1 to \leq 1.5 mg/dL	> 1.5 to \leq 2 mg/dL	> 2 mg/dL
Total Bilirubin, High > 28 days of age	1.1 to < 1.6 x ULN	1.6 to < 2.6 x ULN	2.6 to < 5.0 x ULN	\geq 5.0 x ULN
\leq 28 days of age	See Appendix A. Total Bilirubin for Term and Preterm Neonates	See Appendix A. Total Bilirubin for Term and Preterm Neonates	See Appendix A. Total Bilirubin for Term and Preterm Neonates	See Appendix A. Total Bilirubin for Term and Preterm Neonates
Calcium, High (mg/dL; mmol/L) \geq 7 days of age	10.6 to < 11.5 2.65 to < 2.88	11.5 to < 12.5 2.88 to < 3.13	12.5 to < 13.5 3.13 to < 3.38	\geq 13.5 \geq 3.38
< 7 days of age	11.5 to < 12.4 2.88 to < 3.10	12.4 to < 12.9 3.10 to < 3.23	12.9 to < 13.5 3.23 to < 3.38	\geq 13.5 \geq 3.38

¹⁴ Direct bilirubin > 1.5 mg/dL in a participant < 28 days of age should be graded as grade 2, if < 10% of the total bilirubin.

Chemistries

PARAMETER	GRADE 1 MILD	GRADE 2 MODERATE	GRADE 3 SEVERE	GRADE 4 POTENTIALLY LIFE- THREATENING
Calcium (Ionized), High (mg/dL; mmol/L)	> ULN to < 6.0 > ULN to < 1.5	6.0 to < 6.4 1.5 to < 1.6	6.4 to < 7.2 1.6 to < 1.8	≥ 7.2 ≥ 1.8
Calcium, Low (mg/dL; mmol/L) ≥ 7 days of age	7.8 to < 8.4 1.95 to < 2.10	7.0 to < 7.8 1.75 to < 1.95	6.1 to < 7.0 1.53 to < 1.75	< 6.1 < 1.53
< 7 days of age	6.5 to < 7.5 1.63 to < 1.88	6.0 to < 6.5 1.50 to < 1.63	5.50 to < 6.0 1.38 to < 1.50	< 5.50 < 1.38
Calcium (Ionized), Low (mg/dL; mmol/L)	< LLN to 4.0 < LLN to 1.0	3.6 to < 4.0 0.9 to < 1.0	3.2 to < 3.6 0.8 to < 0.9	< 3.2 < 0.8
Cardiac Troponin I, High	NA	NA	NA	Levels consistent with myocardial infarction or unstable angina as defined by the local laboratory
Creatine Kinase, High	3 to < 6 x ULN	6 to < 10 x ULN	10 to < 20 x ULN	≥ 20 x ULN
Creatinine, High	1.1 to 1.3 x ULN	> 1.3 to 1.8 x ULN OR Increase of > 0.3 mg/dL above baseline	> 1.8 to < 3.5 x ULN OR Increase of 1.5 to < 2.0 x above baseline	≥ 3.5 x ULN OR Increase of ≥ 2.0 x above baseline
Creatinine Clearance¹⁵ or eGFR, Low Report only one	NA	< 90 to 60 ml/min or ml/min/1.73 m ² OR 10 to < 30% decrease from baseline	< 60 to 30 ml/min or ml/min/1.73 m ² OR ≥ 30 to < 50% decrease from baseline	< 30 ml/min or ml/min/1.73 m ² OR ≥ 50% decrease from baseline or dialysis needed

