## **8.2 Clinical laboratory data**

The following clinical laboratory parameters will be measured (see section [12.1](#)):

- At the screening visit,
- On Day 1, Week 1, Week 2, Week 4, Week 6, Week 8 (8 or 12 Week Cohorts), Week 10 (12 Week Cohorts), Week 12 (12 Week Cohorts), safety follow-up visit.

Additional measurements are done on Week 3, Week 5 and Week 7 for alanine aminotransferase (ALT) and aspartate aminotransferase.

**Haematology** parameters will be listed and grouped as follows:

- Red blood cells: haemoglobin (g/L), haemoglobin A1C (mmol/mol) only at screening, hematocrit (fraction of 1), mean corpuscular haemoglobin (MCH) (fmol), mean corpuscular

haemoglobin concentration (MCHC) (mmol/L), mean corpuscular volume (MCV) (fL), mean platelet volume (MPV) (fl), erythrocyte sedimentation rate (mm/h), red distribution width (RDW) (%), reticulocytes (G/L and %) and red blood cell count (RBC) (T/L).

- White blood cells: basophils (G/L and %), eosinophils (G/L and %), lymphocytes (G/L and %), monocytes (G/L and %), neutrophils (G/L and %) and white blood cell count (WBC) (G/L).

- Platelets (G/L).

**Blood chemistry parameters** will be listed and grouped as follows:

- Liver function: alanine aminotransferase (ALT) (IU/L), alkaline phosphatase (IU/L), aspartate aminotransferase (AST) (IU/L), total bilirubin ( $\mu\text{mol/L}$ ) and direct bilirubin ( $\mu\text{mol/L}$ ).

- Renal chemistry: creatinine ( $\mu\text{mol/L}$ ) and blood urea nitrogen (BUN) (mmol/L).

- Electrolytes: calcium (mmol/L), chloride (mmol/L), phosphorus (mmol/L), potassium (mmol/L), sodium (mmol/L) and bicarbonates (mmol/L).

- Metabolism parameters: glucose (mmol/L), cholesterol (mmol/L), triglycerides (mmol/L), lipase (IU/L), uric acid ( $\mu\text{mol/L}$ ) and lactate dehydrogenase (LDH) (IU/L).

- Other parameters: albumin (g/L), creatine kinase (CPK) (IU/L), total protein (g/L), alpha fetoprotein (ug/L) only at screening, Alpha-1 Acid Glycoprotein (g/L) only at screening, Beta natriuretic peptide (BNP) and NT-pro-BNP.

**Coagulation** parameters will be listed and grouped as follows:

- Coagulation parameters: prothrombin time (PT) (s), activated partial thromboplastin time (aPTT) (s) and international normalized ratio (INR).

**Urinalysis** parameters will be listed and grouped as follows:

- Planned urinalysis parameters: dipstick determination of pH, specific gravity, glucose, bilirubin, ketones, leukocytes, nitrite, occult blood, protein and urobilinogen.

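### For a related, clinically significant confirmed eGFR below 30, Protocol 7.5.4 leaves restart open while 4.6.1 ends treatment, and the SAP never derives eGFR

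*Protocol*

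**What the plan says.** **Protocol 7.5.4 (Renal Safety Monitoring).** An eGFR below 30 mL/min/1.73m² must be confirmed by repeat testing. Once it is confirmed, "all study drugs must be interrupted and renal function should be followed as clinically appropriate". On restart: "Recommencement of treatment should be discussed with the Sponsor on a case-by-case basis". These bullets carry no condition on relatedness. A general sentence before them says: "Dosing may continue if the renal complication is considered not to be related to study drug in the opinion of the investigator".

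**Protocol 4.6.1 (Subject Treatment Discontinuation Criteria).** Treatment with AL-335, SMV and ODV "must be permanently discontinued if" any of a list of events occurs. One of them is a "Grade 4 AE or laboratory abnormality at least possibly related to 1 of the study drugs and which is considered clinically significant"; the significance condition applies to laboratory abnormalities only.

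**Protocol Appendix F (DAIDS table), creatinine clearance or eGFR, low.** Grade 4 is a value below 30, or at least a "50% decrease from baseline or dialysis needed".

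**Protocol 10.4.2.** Laboratory values are graded on DAIDS, and Grades 3 and 4 are tabulated.

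**SAP 8.2.** The renal group begins "Renal chemistry: creatinine" and adds only blood urea nitrogen. Neither eGFR nor creatinine clearance appears in the SAP's laboratory parameters or its list of outputs. Protocol Appendix B does not list them either.

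**The concern.** A single laboratory finding can satisfy two dosing rules with different end points: a pause that may be lifted, and a permanent stop. Section 4.6.1 refers to 7.5.1, 7.5.2, 7.5.3 and 7.6 to 7.9, but not to 7.5.4. Section 7.5.4 does not mention 4.6.1. Nothing sets an order of precedence.

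Safety is the primary endpoint. Protocol 7.2.4 codes interruption and withdrawal of drug separately, and SAP 8.1 tabulates treatment-emergent AEs leading to discontinuation of any study drug. If the renal event is reported as an AE, the rule that is followed decides whether it enters that table. The variable that triggers the 7.5.4 rule is also missing from the graded laboratory tables.

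**Working it through.** The plan states no figure to reproduce. The check sets the rules side by side and then tests what graded creatinine would show.

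**Step 1. Where the rules overlap.**

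| Confirmed eGFR finding | 7.5.4 | 4.6.1 |
|---|---|---|
| Below 30, judged unrelated | Interrupt; restart discussed | Grade 4 bullet not met |
| Below 30, at least possibly related, not clinically significant | Interrupt; restart discussed | Grade 4 bullet not met |
| Below 30, at least possibly related, clinically significant | Interrupt; restart discussed | Permanent discontinuation |
| 30 or above, fall of 50% or more, at least possibly related, clinically significant | General monitoring and treatment only | Permanent discontinuation |

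The outcomes diverge in the third row. In the fourth row the two sections have different triggers.

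**Step 2. Which values of 30 or above are Grade 4.** Percent fall to 30 = (baseline − 30) / baseline. The percentage limb is met at or below baseline × 0.5. Baselines start at 60 because Protocol 4.3 excludes creatinine clearance below 60 mL/min.

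| Baseline | Fall to 30 | Grade 4 by percentage at or below |
|---|---|---|
| 60 | 50.0% | 30.0 |
| 75 | 60.0% | 37.5 |
| 90 | 66.7% | 45.0 |
| 100 | 70.0% | 50.0 |
| 120 | 75.0% | 60.0 |

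A value below 30 is Grade 4 on the absolute limit alone, so the overlap in step 1 does not depend on this table. The table shows the extra range: from a baseline of 100, values from 30 to 50 are Grade 4 but above the 7.5.4 threshold. It assumes that baseline and on-study values are on one scale. Entry uses Cockcroft-Gault in mL/min, whereas 7.5.4 uses mL/min/1.73m² and names no formula.

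**Step 3. What graded creatinine captures.** Assume clearance is inversely proportional to creatinine, as in Cockcroft-Gault at fixed age and weight.

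- Large falls: a 50% fall gives a creatinine ratio of 1 / 0.5 = 2.0. Read as a doubling, this is the Appendix F Grade 4 creatinine limit. A fall from 60 or more to below 30 therefore also shows as Grade 4 creatinine. So does a fall from 100 to 50, and the creatinine table cannot tell the two apart.
- Smaller falls: from 65 to 59 the fall is 6/65 = 9.2%. The value moves from the Grade 2 band (below 90 down to 60) to Grade 3 (below 60 down to 30), which is treatment-emergent under the SAP definition. The creatinine ratio is 65/59 = 1.10, a rise of about 10%, well short of the Grade 3 limit of 1.5 times baseline. The other Grade 3 limb (above 1.8 × ULN) would need a baseline creatinine above 1.8/1.10 = about 1.6 × ULN.

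**The case against.** The strongest reply is that the rules work in sequence. Section 7.5.4 sets the immediate action for any confirmed value below 30, whatever the cause, and 4.6.1 then decides permanence for the related and significant subset. Section 7.5.4 grants no right to restart, only a discussion. That reading is reasonable, but the text does not state it, and a site reading 7.5.4 alone would not find it.

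Several stronger conclusions might be inferred, and the documents do not support them:

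- **That every confirmed eGFR below 30 is in conflict.** Section 4.6.1 needs both relatedness and clinical significance; other cases fall under 7.5.4 alone.
- **That sites would treat the same event differently as a matter of course.** Restart goes through the Sponsor, and Protocol 5.4 allows no interruption without consulting the Medical Monitor. Much of the remaining variation comes from judgements that 4.6.1 deliberately requires.
- **That 7.5.4 contradicts itself.** The sentence allowing dosing to continue is a general permission, and the eGFR bullet is a specific requirement that naturally limits it. A linking phrase would help, but this is editorial.
- **That nothing happens at 30 or above under 7.5.4.** Close monitoring of creatinine and eGFR, and appropriate treatment of complications, still apply.
- **That the safety tables are blind to renal toxicity.** SAP 8.2 grades, lists and plots creatinine, and step 3 shows that this captures most large falls.
- **That SVR12 is materially affected.** The documents give no rate for these events. With 123 subjects dosed by 6 February 2017, Protocol 1.2.1.2 reports no clinically significant laboratory finding suggesting a safety concern.

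**Conclusion.** The point holds in a limited form. For a confirmed eGFR below 30 that is at least possibly related and considered clinically significant, 7.5.4 and 4.6.1 lead to different outcomes, with no cross-reference or precedence. The percentage limb in Appendix F extends 4.6.1 to values of 30 or above, where 7.5.4 has no specific dosing step.

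On the analysis side, the SAP does not derive the variable on which 7.5.4 acts. Graded creatinine is a good but incomplete substitute: it does not isolate subjects with eGFR below 30, and it misses some Grade 3 eGFR events.

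The number of subjects affected cannot be estimated from the documents and may be small. The overlap below 30 rests on the text alone. The creatinine comparison rests on inverse proportionality at fixed age and weight, and on one scale for baseline and follow-up. No view is taken on which dosing rule is right.

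**What to change.** **Protocol.** Reconcile and cross-reference 4.6.1, 7.5.4 (including its sentence on continuing dosing) and the Appendix F grades for creatinine clearance or eGFR. The text should say which section governs when both apply, and how a Grade 4 fall that stays at 30 or above is handled. The sponsor decides the clinical rule.

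**SAP 8.2.** Derive creatinine clearance or eGFR by a named formula, and add it to the DAIDS treatment-emergent grade tables and the Grade 3/4 listings. For Cockcroft-Gault, which Protocol 4.3 uses at entry and the Appendix F footnote names, the inputs (creatinine, age, sex and weight) are already collected. Weight is scheduled only at screening and the last treatment visit, so the SAP should say which weight is used. If a different formula is meant for 7.5.4, name it there too, so that the tables show the value on which the dosing decision was made.

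**Cost.** Protocol wording and one derived variable; no new data collection.
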